3. STUDY METHODS AND PROCEDURES

3.1 Study Treatment/Intervention

Patients assigned to the intervention group will undergo BFR exercises in addition to the standard rehabilitation protocol. BFR therapy will be administered at an INOVA physical therapy location by a certified physical therapist that is trained in BFR modalities. Therapists will follow a standardized ACL rehabilitation protocol (see appendix), which consists of 2-3 therapy sessions per week following surgery. BFR exercises will begin after the surgical incision has healed and post-operative swelling is minimized. This generally occurs two weeks post-operatively.

3.2 Control Group

Patients assigned to the control group will complete a standardized ACL rehabilitation protocol that does not include BFR therapy (see appendix). Similar to the treatment group, the protocol will incorporate 2-3 therapy sessions per week following surgery, which will be administered by a certified physical therapist at an INOVA physical therapy location.

3.3 Randomization

Upon enrollment in the study, before their surgery, patients will be randomly assigned to the treatment group (75 subjects) or control group (75 subjects) using a random number generator.

3.4 Endpoints/Outcomes Measurement

3.4.1 Primary Outcomes

The main objective is to determine whether BFR therapy has an effect on the functional outcomes of patients recovering from ACL reconstruction. Functional outcome measures will include Knee Injury and Osteoarthritis Outcome Score (KOOS), International Knee Documentation Committee Subjective Knee Evaluation Form (IKDC), Limb Symmetry Index (LSI), knee extension strength using a dynamometer, and return to sport.

3.4.2 Secondary Outcomes

The secondary objective is to determine if BFR exercises are associated with adverse effects such as numbness, tourniquet-site pain, and bruising.

3.5 Consent/Accent

Patients will be assented with their parent(s)/guardian(s) consent. A witness will confirm the agreement to enroll and patients will always be required to be accompanied by their parent/guardian at each visit, if they are under the age of 18. If the patient should turn 18 during the course of the study (13-17 years old at enrollment), they will be re-consented as an adult at that time. Patients will not be coerced to participate in this research study and they will be informed that the quality or type of care received at Inova will not be affected by their decision to participate in this study.

Individuals who are able to assent/consent patients are Drs. [name], [name], [name] or [name]. Drs. [name] and [name] are the participating surgeons on this study. Both are board certified Orthopaedic Surgeons who are fellowship-trained in Sports Medicine. Both surgeons are skilled in conducting clinical examinations, reviewing diagnostic imaging, performing surgery, and post-operative management. [name] is a chief orthopaedic surgery resident at Georgetown University. All of these individuals are qualified to speak on the surgical and study procedures. All have completed the WIRB-Copernicus Group Academy (WCGA) research ethics training and have completed particular modules in obtaining informed consent.

Separate HIPAA authorization will be obtain from each patient or parent(s)/guardian(s) of the patient. Parent(s)/guardian(s) will consent and provide HIPAA authorization, in addition to, getting the child's assent. Adult patients will only need to provide HIPAA authorization as well as consent for participation in the study.

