Outcome measures will include Knee Injury and Osteoarthritis Outcome Score (KOOS), International Knee Documentation Committee Subjective Knee Evaluation Form (IKDC), Limb Symmetry Index (LSI), thigh circumference, and return to sport. Baseline scores will be obtained prior to surgery when applicable. Outcomes will be measured at designated time intervals for 2 year following surgery.

Statistical Methodology: Data will be reviewed by a trained statistician. Repeated-measures analysis of variance (ANOVA) will be used to evaluate all patient-reported outcome surveys at multiple time points. All statistical tests will use two-tailed hypothesis testing with the statistical significance a priori set at alpha, α , is equal to 0.05

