2.4 Number of Subjects

The goal is to include 150 subjects in the study, which will be divided into 75 patients in the treatment group and 75 patients in the control group.

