2.6 Recruitment

Recruitment will include all patients that meet the inclusion criteria who choose to undergo ACL reconstruction with an INOVA sports medicine fellowship-trained orthopedic surgeon.

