 - International Knee Documentation Committee Subjective Knee Evaluation Form (IKDC)
 - VAS
 - Completed at 3 month intervals
 - Baseline (prior to surgery)
 - 3 months, 6 months, 9 months, 12 months, 24 months
- Limb Symmetry Index (LSI)
 - Consists of 4 assessments:
 - Single hop for distance, triple hop for distance, cross-over hop for distance, 6 meter hop for time
 - Compare operative leg vs. non-operative leg
 - Completed at 3 month intervals after surgery
 - 3 months, 6 months, 9 months, 12 months
- Quadriceps muscle assessment
 - Thigh circumference
 - Compare operative leg vs. non-operative leg
 - Completed at 3 month intervals
 - Baseline (prior to surgery)
 - Just for thigh circumference
 - 3 months, 6 months, 9 months, 12 months
- Return to sport
 - Defined as the date that patient is cleared for return to all sports without restriction by their physician utilizing an objective return to play criteria.

Adverse Effects:

- Therapist-completed survey of BFR:
 - Administered during PT session
 - Assesses for bruising, tourniquet-site pain, numbness, compartment syndrome, rhabdomyolysis
- Miscellaneous complications:
 - Ie: DVT/PE, reinjury, return to operating room, etc.
 - Will be recorded during office visits

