4. STATISTICAL CONSIDERATIONS/DATA ANALYSIS

4.1 Sample Size

We are currently aware of no studies that use KOOS, IKCD scores, limb symmetry index, or return to play for BFR therapy after ACL reconstruction. However, studies [10, 11, 12, 13] of similar populations have found OOS, IKDC, LSI, RTP values of 91.5, 87.5, 79%, and 209 days, respectively. Using those estimates, a power analysis was done and sample size of 150 provides enough power (80%, with an alpha of 0.05) to detect clinically significant changes in these values, while simultaneously accounting for any potential loss-to-follow-up or early withdrawal from the study.

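### Operating surgeon is neither recorded nor used in any analysis, although two surgeons take part and return to sport is a physician's clearance date; a prespecified surgeon term would be a cheap gain in precision.

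*Combined protocol and SAP*

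**What the plan says.** - **Surgeons.** Section 3.5 names two individuals (names removed) who "are the participating surgeons on this study", and describes both as having sports medicine fellowship training. Section 2.6 recruits eligible patients "who choose to undergo ACL reconstruction with an INOVA sports medicine fellowship-trained orthopedic surgeon".
- **Allocation.** Under 3.3, at enrolment and before surgery, "patients will be randomly assigned to the treatment group (75 subjects) or control group (75 subjects) using a random number generator". No stratification factor is given.
- **Return to sport.** Section 3.4.1 lists it among the primary outcomes. Section 3.6 defines it as the date the patient is "cleared for return to all sports without restriction by their physician", and adds that the physician applies an objective set of return-to-play criteria. The supplied text does not give those criteria.
- **Data recorded.** Section 3.6 lists graft type, fixation, concomitant injuries and concomitant procedures in detail. It has no field for surgeon.
- **Analysis.** The abstract plans repeated-measures ANOVA for the patient-reported surveys and names no covariates. Section 4.2 adds descriptive statistics and measures of association for unnamed predictors of function and return to sport. Surgeon appears in neither place.

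**The concern.** Surgeons may differ in technique and in how readily they clear a patient for unrestricted sport. If they do, and the analysis ignores surgeon, two things follow.

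1. The between-surgeon difference goes into the error variance and costs some power.
2. Because allocation is not stratified, one arm may by chance contain more patients of the surgeon who clears earlier. In that realised trial, part of the difference in clearance date between arms would reflect the surgeon mix and not blood flow restriction.

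Return to sport is the outcome most exposed, since it is itself a physician's decision. For KOOS and IKDC (patient-reported) and LSI (hop testing), clearance habits play no part. Only differences in technique or aftercare could act there.

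Adjustment would be valid. Patients are recruited through the surgeon they have chosen and are randomised before the operation (2.1, 2.6, 3.3), so the intended operating surgeon is known before allocation.

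**Working it through.** **The plan's own figure.** Section 4.1 says that a "sample size of 150 provides enough power (80%, with an alpha of 0.05) to detect clinically significant changes in these values". It gives reference values (209 days for return to play, for example) but no SD, target difference or dropout rate, so 150 cannot be reproduced. Working backwards, with 75 per arm, two-sided alpha 0.05 and 80% power, the detectable difference is (1.960 + 0.842) × √(2/75) = 0.457 SD with no dropout.

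**Inputs**
- From the documents: 75 per arm (2.4, 3.3), two-sided alpha 0.05 (abstract), two surgeons (3.5).
- Assumed, because the documents give nothing: caseload share p = 0.5; difference between surgeons in mean clearance time δ = 14, 21 or 45 days; within-surgeon SD σ = 45 or 60 days; arm difference to detect = 21 days. A comparison of means stands in for the return-to-sport analysis, which the plan does not specify.

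**Step 1: chance imbalance in surgeon mix.** The SD of the between-arm difference in surgeon share is √(p(1−p) × 2/75) = √(0.25 × 2/75) = 8.2 points. The 95% range is 1.96 × 8.2 = ±16 points. With a 70:30 caseload it is ±14.7 points.

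**Step 2: shift in the estimate at that imbalance.** This is 0.16 × δ:
- 14 days: 2.2 days
- 21 days: 3.4 days
- 45 days: 7.2 days

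**Step 3: variance and power.** Ignoring surgeon, the variance is σ² + p(1−p)δ²; adjusting for surgeon, it is σ². Surgeon's share of the variance is p(1−p)δ² / (σ² + p(1−p)δ²). For example, at δ = 45 and σ = 45 it is 506.25 / (2025 + 506.25) = 20%. Two-sample t-test power for a 21-day difference:

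| δ (days) | σ (days) | Surgeon share of variance | Power unadjusted | Power adjusted | Gain (points) |
|---|---|---|---|---|---|
| 14 | 45 | 2.4% | 80.1% | 81.0% | 0.9 |
| 21 | 45 | 5.2% | 79.0% | 81.0% | 2.1 |
| 45 | 45 | 20.0% | 71.9% | 81.0% | 9.1 |
| 14 | 60 | 1.3% | 56.2% | 56.7% | 0.6 |
| 21 | 60 | 3.0% | 55.5% | 56.7% | 1.3 |
| 45 | 60 | 12.3% | 51.4% | 56.7% | 5.4 |

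The gap between the upper and lower halves of the table comes from the assumed SD. The effect of adjustment is the last column only.

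**Step 4: the same in SD units.** Let g be the surgeon gap in within-surgeon SDs. At a true arm difference of 0.457 SD, with a 50:50 caseload and no adjustment:
- g = 0.3: power 79.1%, total N for 80% power 154
- g = 0.5: power 77.6%, total N 160
- g = 1.0: power 70.7%, total N 188

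**Step 5: error rate.** Over 20,000 simulated trials with no arm effect and no adjustment, type I error was 5.2% at g = 0.5 and 5.1% at g = 1.0, and the mean arm difference was essentially zero. Conditional on a trial with a 16-point imbalance, the calculated type I error is 5.7%, 6.9% and 11.4% at g = 0.3, 0.5 and 1.0.

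**The case against.** **Randomisation already protects the comparison.** This is correct. A reader might infer that omitting surgeon biases the result. It does not: allocation is random, the unadjusted estimate is unbiased, and type I error stays near 5% over repeated trials. What remains is lost precision and chance imbalance in one trial, as with any prognostic covariate left out.

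**The protocol has its own control on clearance.** Section 3.6 requires objective criteria, and rehabilitation is standardised in both arms (3.1, 3.2). Both should narrow surgeon differences. This carries weight against the large-gap scenarios: 45 days is about 22% of the plan's 209-day reference value (45/209). It does not close the matter, because the criteria are not set out in the supplied text and the timing of testing and sign-off may still vary.

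**The clearing physician may not be the surgeon.** The documents do not say. If another physician clears patients, a term for operating surgeon will not remove that variation.

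**Technique is partly captured.** Graft, fixation and procedures are recorded, and 4.2 plans measures of association. But 4.2 names no predictors, and none of this is tied to the arm comparison.

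**The data are not lost.** Section 4.3.1 plans review of Epic for clinic and surgery information, so surgeon can probably be recovered. The gap is in prespecification.

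**Do 2.6 and 3.5 conflict?** A reader might think so, since one describes a class of surgeons and the other names two. The two are described as fellowship-trained in sports medicine and so fit the 2.6 description. No contradiction is shown.

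**Conclusion.** The point holds as a minor matter of precision. Two surgeons take part, allocation is not stratified by surgeon, surgeon is not recorded, and no analysis uses it, while one primary outcome is a physician's clearance date.

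For return to sport the likely gain from adjustment is about 0.5 to 2 points of power if surgeons differ by 14 to 21 days. Nine points needs a 45-day gap with SD 45, a full within-surgeon SD between two surgeons, and should not be taken as typical. Every surgeon gap, SD, caseload split and target difference behind these figures is assumed.

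The day-based figures concern return to sport only. The documents give no basis for sizing a surgeon effect on KOOS, IKDC or LSI, so the benefit there is unquantified. Nor do they support calling the unadjusted analysis biased: a 16-point imbalance would matter in the trial where it occurred, but it is not a systematic error.

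**What to change.** 1. In 3.6, add operating surgeon to the intraoperative data. It should be available from the operative record or Epic.
2. In 4.2, prespecify that the return-to-sport comparison is stratified by operating surgeon.
3. In 4.2, include surgeon as a fixed effect in the KOOS, IKDC and LSI arm comparisons, described as a low-cost precision term whose benefit is not quantified.

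The cost is one data field and one degree of freedom with two surgeons, slightly more if others operate. No extra patients, visits or staff are needed. If the surgeons behave alike, little is gained. Writing the term in now also avoids the challenge that a surgeon adjustment chosen after seeing the data would attract.

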3.6 Data Collection

The following data will be recorded:

Demographics:

- Gender
- Age at time of surgery
- BMI at time of surgery
- Sports participation (if applicable):
 - Type of sport
 - ie: football, soccer, baseball, track, etc.
 - Level of competition
 - High school
 - Collegiate

- Professional
 - Recreational
- Prior knee injuries:
 - Eg. ipsilateral/contralateral ACL tears, meniscal injuries, chondral injury
- Smoking status
 - Non-smoker
 - Former smoker
 - Smoker (number of packs per day)
- Diabetes

Injury Data:

- Laterality of injury
 - Left
 - Right
- Date of injury
- Time from injury to surgery
- Mechanism of injury:
 - Contact
 - Non-contact (ie: twisting)
- Concomitant ligament injury observed on MRI:
 - Ligament
 - Medial Collateral Ligament (MCL)
 - Lateral Collateral Ligament and/or Posterolateral corner (LCL/PLC)
 - Posterior Cruciate Ligament (PCL)
 - Severity of injury
 - Grade 1: (minor sprain) high signal is seen medial (superficial) to the ligament, which looks normal
 - Grade 2: (severe sprain or partial tear) high signal is seen medial to the ligament, with high signal or partial disruption of the ligament
 - Grade 3: complete disruption of the ligament
 - Note: Concomitant ligament injury *requiring reconstruction* is an exclusion criteria

Intraoperative Data:

- Type of ACL graft:
 - Bone-patellar tendon bone (BTB) autograft
 - Hamstring tendon (HS) autograft
 - Allograft
- ACL graft fixation (interference screws, suspensory fixation)
- Concomitant injuries observed intraoperatively
 - Meniscal tear
 - Medial vs. Lateral
 - Type of tear (longitudinal, radial, degenerative, bucket-handle)
 - Chondral injury
 - Location
 - Medial compartment
 - Lateral compartment
 - Patellofemoral joint
 - Severity (Outerbridge Classification)
 - Grade 0: normal
 - Grade I: cartilage with softening and swelling

- Grade II: partial-thickness defect with fissures on the surface that do not reach subchondral bone or exceed 1.5 cm in diameter
 - Grade III: fissuring to the level of subchondral bone in an area with a diameter more than 1.5 cm
 - Grade IV: exposed subchondral bone
- Concomitant procedures performed:
 - Meniscectomy
 - Partial vs. Complete
 - Medial vs. Lateral
 - Meniscal repair
 - Chondroplasty
 - Microfracture
 - Note: Concomitant procedure requiring delayed weightbearing is an exclusion criteria

Outcome Data:

- Validated patient reported outcomes:
 - Surveys:
 - Knee Injury and Osteoarthritis Outcome Score (KOOS)
 - International Knee Documentation Committee Subjective Knee Evaluation Form (IKDC)
 - VAS
 - Completed at 3 month intervals
 - Baseline (prior to surgery)
 - 3 months, 6 months, 9 months, 12 months, 24 months
- Limb Symmetry Index (LSI)
 - Consists of 4 assessments:
 - Single hop for distance, triple hop for distance, cross-over hop for distance, 6 meter hop for time
 - Compare operative leg vs. non-operative leg
 - Completed at 3 month intervals after surgery
 - 3 months, 6 months, 9 months, 12 months
- Quadriceps muscle assessment
 - Thigh circumference
 - Compare operative leg vs. non-operative leg
 - Completed at 3 month intervals
 - Baseline (prior to surgery)
 - Just for thigh circumference
 - 3 months, 6 months, 9 months, 12 months
- Return to sport
 - Defined as the date that patient is cleared for return to all sports without restriction by their physician utilizing an objective return to play criteria.

Adverse Effects:

- Therapist-completed survey of BFR:
 - Administered during PT session
 - Assesses for bruising, tourniquet-site pain, numbness, compartment syndrome, rhabdomyolysis
- Miscellaneous complications:
 - Ie: DVT/PE, reinjury, return to operating room, etc.
 - Will be recorded during office visits

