2. STUDY DESIGN AND SUBJECT SELECTION

2.1 Study Type

This will be a single-center randomized control trial. Patients will be recruited, consented, enrolled, and randomized before their ACL reconstruction surgery

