4.2 Method of Data Analysis

Descriptive statistics including measures of location (mean, median, percentile) and spread (standard deviation, ranges) will be computed for continuous variables. Frequency distributions will be computed for categorical data. Measures of association will be used to determine positive and negative predictors of functional outcomes and return to sport.

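### Return to sport is a primary outcome held only as a clearance date, with no between-arm comparison named and no rule for patients who never get a date

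*Combined protocol and SAP*

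**What the plan says.** Section 3.4.1 lists return to sport among the primary functional outcomes, and section 1.1 hypothesises that it comes sooner with BFR. Section 3.6 gives the only definition: "Defined as the date that patient is cleared for return to all sports without restriction by their physician utilizing an objective return to play criteria". Section 4.1 gives its planning value as the last item in "RTP values of 91.5, 87.5, 79%, and 209 days, respectively".

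Three statements on analysis could bear on it:

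- Section 4.2, on continuous data: "Descriptive statistics including measures of location (mean, median, percentile) and spread (standard deviation, ranges) will be computed for continuous variables". The next sentence provides frequency distributions for categorical data.
- Section 4.2, on predictors: "Measures of association will be used to determine positive and negative predictors of functional outcomes and return to sport". Treatment arm is not mentioned.
- The Abstract names the only inferential test: "Repeated-measures analysis of variance (ANOVA) will be used to evaluate all patient-reported outcome surveys at multiple time points". Clearance by a physician is not a survey. The Abstract also sets two-tailed testing at 0.05 for all tests.

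On timing, section 2.1 states "Patients will be recruited, consented, enrolled, and randomized before their ACL reconstruction surgery". The Abstract lists return to sport among the outcome measures and says outcomes are measured for two years after surgery. Loss to follow-up appears only as an allowance in section 4.1, and re-injury only as a recorded complication in section 3.6. Sport is recorded as "Sports participation (if applicable" and is not an inclusion criterion.

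**The concern.** Limb symmetry and knee strength also lack a named test. Return to sport differs because an uncleared patient has no value at all. The same is true of a patient lost before clearance, and of one re-injured before clearance unless cleared later. Patients with no sport may also have no date.

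A mean or test of days therefore drops these patients without anyone having decided to. Clearance happens after randomisation and may be affected by treatment. If the arms differ in the share cleared, comparing days among the cleared no longer compares the groups as randomised. It can miss a benefit that lies in how many patients are cleared, or show a gain in days where fewer are cleared. If the method is chosen after the data are seen, the result of a primary outcome can depend on that choice.

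**Working it through.** **1. The plan's own figure.** Section 4.1 says 150 patients give 80% power at 0.05. For return to sport this can be neither reproduced nor refuted: the documents give no SD, difference, hazard ratio, share cleared or dropout rate. Solved backwards for a two-sided comparison of means, the detectable standardised difference is (1.960 + 0.8416) × √(2/75) = 2.8016 × 0.1633 = 0.457. With assumed SDs of 30, 60, 90 and 120 days that is 13.7, 27.4, 41.2 and 54.9 days. If 20% have no date (assumed; 60 per arm), the figures become 15.3, 30.7, 46.0 and 61.4 days.

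**2. How far the method matters.** From the documents: 75 per arm, two-sided 0.05, 209 days (used as the control median) and two years of follow-up. Assumed: lognormal clearance times with log-SD 0.3, the shares cleared, and a 10% faster return (median 0.9 × 209 = 188 days). Uncleared patients are censored at 730 days. Each setting has 10,000 simulated trials. Days are compared by Welch t test among the cleared; RM is the restricted mean from the Kaplan-Meier curve. Entries are percent of trials significant.

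| Scenario (control v BFR cleared) | Days among cleared | Log-rank | RM to 12 months | RM to 24 months |
|---|---|---|---|---|
| Same timing, 85 v 85 | 4.8 | 5.0 | 5.4 | 4.9 |
| Same timing, 85 v 85, 10% random loss | 4.9 | 5.1 | 5.3 | 5.3 |
| Same timing, 80 v 85 | 4.9 | 10.8 | 9.0 | 12.2 |
| Same timing, 75 v 85 | 4.9 | 28.6 | 21.4 | 33.0 |
| Same timing, 70 v 85 | 5.1 | 52.6 | 38.4 | 58.1 |
| BFR 10% faster, 95 v 95 | 52.7 | 30.6 | 44.3 | 18.9 |
| BFR 10% faster, 85 v 85 | 47.9 | 16.0 | 27.8 | 9.6 |
| BFR 10% faster, 70 v 70 | 41.5 | 9.5 | 18.0 | 7.2 |

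Hand check of the 47.9: about 0.85 × 75 = 63.75 are cleared per arm. On the log scale z = 0.1054 / (0.3 × √(2/63.75)) = 1.98, so power is about Φ(1.98 − 1.96) = 51%, close to the simulated value in days.

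The 5% for days in the same-timing rows is by construction, since timing does not differ there. The table shows that no method wins throughout. Days among the cleared cannot see a difference in the share cleared. Log-rank, and the restricted mean to 24 months, lose power when equal shares are eventually cleared, because the curves separate and then rejoin.

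**3. Sensitivity.** At 70% v 85% with the same timing, days and log-rank give 4.5 and 52.6 with log-SD 0.2, 5.2 and 51.3 with log-SD 0.5, and 4.8 and 52.2 with median 240. Other 15-point gaps give 4.9 and 45.0 (55% v 70%) and 5.1 and 66.3 (80% v 95%).

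**4. Direction.** In a separate run (normal times, SD 60 days, 4,000 trials), 85% of controls are cleared at a mean of 209 days and 70% of BFR patients at 190. Days among the cleared then favour BFR by 18.5 on average (39% significant), although fewer BFR patients are cleared.

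**5. What log-rank can detect.** At 80% power with equal arms, HR = exp(2 × 2.8016 / √events): 1.58 with 150 clearances, 1.67 with 120 and 1.73 with 105 (70% of 150). This assumes proportional hazards, which the scenarios above do not generally satisfy.

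**The case against.** Four objections have force.

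- A reader might infer that time origin and collection window are missing. The documents do not support that: the Abstract measures outcomes, including return to sport, for two years after surgery, and section 2.3 also counts follow-up from surgery. Because randomisation comes before surgery, one clarifying line is still worth adding.
- A reader might infer that the plan intends to compare cleared patients only. It does not say so, and the frequency distributions in section 4.2 could tabulate cleared against not cleared. That supplies a description, not a comparison of the arms.
- Arm could be one of the predictors in section 4.2. It is not said to be, and no test or effect measure is named.
- The hypothesis is about faster return, and when only timing differs the days-only comparison has more power than log-rank (48% v 16% at 85% cleared). This stands. It rules out a general claim that log-rank is better, but strengthens the case for fixing the method in advance.

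The missing test name is partly a plan-wide omission. What is specific here is the treatment of patients without a date.

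**Conclusion.** The point holds as a recommended change. A primary outcome has no specified comparison of the randomised groups and no rule for patients without a clearance date; a days summary, followed as written, describes only those cleared.

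The size is conditional. In the settings examined, the chance of a significant result moves between 5% and 53% (same timing, 70% v 85% cleared) or between 48% and 16% (10% faster, 85% cleared in both arms) for days among the cleared against log-rank. All clearance rates and spreads are assumed. If clearance is equal and loss is random, there is no bias. The figures therefore do not show that this trial will be biased, nor that 150 patients are too few.

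**What to change.** In section 4.2:

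- Define the outcome as time from surgery to clearance, followed to 24 months and analysed by assigned arm in all randomised patients who have surgery. Report by arm those randomised but not operated on.
- State whether patients found at surgery to need an excluded procedure stay in, given section 3.6: "Note: Concomitant procedure requiring delayed weightbearing is an exclusion criteria".
- Censor uncleared patients at 24 months. Censor lost patients at the last office visit or record at which clearance status was known. A returned survey is not enough, because the documents do not say that surveys record clearance. Add a sensitivity analysis for informative loss.
- Do not censor at re-injury; use a later clearance date if there is one.
- State how patients with no sport are handled, using participation recorded before randomisation.
- Show Kaplan-Meier cumulative clearance, and the proportion cleared by 12 and 24 months, by arm.
- Before data are seen, name one between-arm comparison: log-rank with hazard ratio, or restricted mean time at a stated horizon. Days among the cleared may be reported as descriptive only.

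In section 4.1, state what 75 per arm detects on the chosen scale; the hazard ratios in step 5 of the working serve for log-rank.

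The cost is mainly wording and some extra analysis, plus a check that each visit record shows clearance status. The real price is lower power than a days-only comparison if equal shares are cleared and only timing differs. The horizon matters too: the restricted mean to 12 months does better than to 24 months when timing differs (28% v 10% at 85% cleared), and worse when the share cleared differs (38% v 58% at 70% v 85%).

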4.3 Data Storage

4.3.1 Data Management

All records related to a subject's involvement in this research study will be stored in a locked file cabinet on the second floor of the Inova Orthopaedic and Sports Medicine Group. The subject's identity of these records will be indicated by a case number rather than by name, and the information linking these case numbers with their identity will be kept separate from the research records. Only the researchers listed on the first page of this form and their staff will have access to a subject's research records.

Data will be collected in a standardized fashion by the physicians and office staff. No publication or reports will contain any identifying information about individual participants. PI, co-investigators, and research staff will review medical records, private office charts, and obtain new questionnaires from patients. The radiology report will be reviewed for exclusion criteria. Only IRB-approved study members will have access to the data and study materials. Epic clinical information databases will be reviewed for information gathered from clinic visits and/or surgery.

Data accuracy and protocol compliance will be assessed during standard Quality Control operations, to include compliance checks and regular data verification. Protocol deviations will be reported to the IRB as policy. Noncompliance will be reported to the IRB as standard.

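### Return to sport, a primary outcome, is the date the patient's own physician gives clearance under criteria called objective, and nothing in the plan keeps the arm from that physician

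*Combined protocol and SAP*

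**What the plan says.** Section 3.4.1 (Primary Outcomes) lists five functional measures: KOOS, IKDC, LSI, "knee extension strength using a dynamometer, and return to sport". Section 3.6 gives the date of return to sport as when the patient is "cleared for return to all sports without restriction by their physician utilizing an objective return to play criteria".

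On who might know the arm:

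- Section 3.3: "Upon enrollment in the study, before their surgery, patients will be randomly assigned to the treatment group" or to control. It does not say who is told.
- Section 3.5: the participating surgeons are among those who may take consent, and their post-operative role is described: "Both surgeons are skilled in conducting clinical examinations, reviewing diagnostic imaging, performing surgery, and post-operative management".
- Section 4.3.1: "Data will be collected in a standardized fashion by the physicians and office staff". The investigators and research staff also review medical records and office charts.
- Section 3.1: "BFR therapy will be administered at an INOVA physical therapy location". Section 2.2 places follow-up at the orthopedic offices, described separately from the therapy facility.

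Section 3.6 names no assessor for the hop tests or thigh circumference, and no section names one for dynamometry. The document contains no statement on masking of patients, therapists, physicians, assessors or the statistician.

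**The concern.** Section 1.1 hypothesises a faster return to sport with BFR, and section 1.2 expects BFR to do better on every measure. The person who sets the date of this primary outcome is a treating clinician, and nothing in the plan prevents that person from knowing the arm.

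Calling the criteria objective limits discretion over whether a patient qualifies. It does not fix when the criteria are checked or when clearance is then given, and it is clearance that is dated. Expectation could therefore create or inflate a difference in the hypothesised direction.

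Hop tests and dynamometry depend on effort and encouragement, and both feed primary outcomes (LSI and knee extension strength). Thigh circumference can also be affected by the measurer, but it is not in the section 3.4.1 list. A larger sample does not cure this kind of error: it narrows the standard error around a shifted mean.

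**Working it through.** **The plan's own figure.** Section 4.1 states 150 patients for 80% power at alpha 0.05, with an allowance for loss to follow-up. It gives a reference return-to-play value of 209 days but no SD, target difference or dropout rate. The figure therefore cannot be reproduced; it can only be solved backwards. A total of 150 corresponds to a standardised difference of 0.46 with no dropout (75 per arm), or 0.50 with 15% dropout (63 per arm; 63/0.85 = 74.1, rounded up to 75).

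**Inputs for the illustration.**
- From the documents: 75 per arm (2.4), two-sided alpha 0.05 (abstract), 80% power (4.1).
- Assumed: SD of return-to-sport time of 30, 45, 60 or 90 days; a shift of 7 or 14 days in one arm's mean clearance date caused by knowledge of the arm; comparison of mean days. Section 4.2 names no specific analysis for this outcome.

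**Detectable difference.** (1.960 + 0.842) × SD × √(2/75) = 0.457 × SD.

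**False-positive rate with no true effect and a shift of b days.** SE = SD × √(2/75) = 0.1633 × SD. By normal approximation, P(reject) = Φ(b/SE − 1.96) + Φ(−b/SE − 1.96).

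Example for SD 30 and b = 7: SE = 4.90, b/SE = 1.43, and Φ(−0.53) plus a negligible second term gives 29.8%.

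| Assumed SD (days) | SE (days) | Detectable difference (days) | False-positive rate, 7-day shift | False-positive rate, 14-day shift |
|---|---|---|---|---|
| 30 | 4.90 | 13.7 | 29.8% | 81.5% |
| 45 | 7.35 | 20.6 | 15.9% | 47.8% |
| 60 | 9.80 | 27.4 | 11.0% | 29.8% |
| 90 | 14.70 | 41.2 | 7.6% | 15.9% |

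With no shift the rate is 5% in every row. A 7-day shift is 7/41.2 = 17% to 7/13.7 = 51% of the detectable difference.

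**If 20% are lost** (75 × 0.8 = 60 per arm), the detectable difference becomes 15.3 to 46.0 days, and the 7-day rate runs from 24.8% (SD 30) down to 7.1% (SD 90). The picture is the same.

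**The case against.** The strongest reply is that the plan does limit discretion, since clearance must rest on objective criteria. They may be written down elsewhere: sections 3.1 and 3.2 cite an appendix for the rehabilitation protocol, which is not in the document at hand. That stands as far as it goes, and how much discretion remains cannot be judged. It does not answer the gap between meeting the criteria and being cleared.

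Four stronger readings are tempting, and the documents do not support them:

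- **That the clearing physician and office staff know the arm.** The document is silent. Consent precedes assignment, so taking consent does not reveal it. What can be said is that nothing keeps the arm from them.
- **That office staff take the limb measures.** Section 4.3.1 is a general sentence on data collection. If hop tests or dynamometry are done at the therapy site, masking the office would not mask them.
- **That masking the office is free.** DVT/PE is among the listed BFR risks (5.1), and complications of that kind are recorded at office visits (3.6). Adverse event reports must give therapy provided and relationship to protocol (7). Staff review charts (4.3.1), and there is no funding (8). These need controls. They do not make masking unworkable, because the BFR side-effect survey is completed by therapists during therapy sessions and adverse events are reported by the research coordinator.
- **That the bias would match the effect sought.** Suppose 15% or 20% of the BFR arm were cleared one 90-day visit earlier. The mean would shift by 0.15 × 90 = 13.5 or 0.20 × 90 = 18 days. Those rates have no source, and section 3.6 does not tie clearance to study visits. At SDs of 60 to 90 days the shift is only 13.5/41.2 = 33% to 18/27.4 = 66% of the detectable difference.

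**Conclusion.** The point holds in this form: a primary outcome is dated by a treating physician's decision, no masking is described, and the criteria behind the decision are not set out in the document. Following the plan as written leaves that outcome open to expectation bias in the hypothesised direction. The same exposure applies to LSI and knee extension strength to the extent that their unnamed assessors know the arm.

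The size is illustrative, because the SDs and the shifts are assumptions. A one-week shift would be enough to lift the false-positive rate from 5% to roughly 8% to 30%. The documents give no evidence that such a shift will occur. The change is worth making because treatment and follow-up are already separated by site, so the protection is available at low cost.

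**What to change.** 1. **Section 3.3.** Release the assignment only to the treating therapy site and to the research coordinator who handles adverse event reports. Keep it from the clearing physician and from existing staff who take LSI, dynamometer or thigh measurements where these are done at the office. Ask patients not to disclose their arm at office visits. Log any unmasking, which is always allowed for safety.
2. **Section 3.6.** Name who performs each limb measure and where. At each existing visit, record for every patient whether each element of the plan's own return-to-play criteria was met. Analyse the first visit at which all were met alongside the clearance date. Clearance itself stays with the physician, and no clinical threshold changes.

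**Cost.** The change needs protocol wording, a different recipient of the assignment, one additional form at existing visits, and some administration to control chart access and route adverse event information. The sample size is unchanged and no extra assessor is needed.

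**Limits.** Masking will be partial because of chart access, complication recording and patient disclosure. The criteria-met date is only as fine as the visit schedule. KOOS and IKDC, reported by patients who know their arm, are not protected.
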